#### **4.5.2.3 Number of bleeding sites associated with abutment teeth at Week 6 and Week 12**

At each post-baseline visit, number of bleeding sites associated with abutment teeth will be analyzed using an ANCOVA model with treatment group, gender, denture material type (acrylic or cobalt chrome), and baseline mean overall MGI score (low, high) as factors and the baseline number of bleeding sites (associated with abutment teeth) as a covariate. The adjusted means and SEs of the two treatment groups together with the treatment difference, SE, 95% confidence interval of the difference, between-group p-value and the proportionate reduction will be provided in [Table 14.2.3.2.2](#) for the mITT population.

The proportionate reduction will be calculated as:

- Proportionate reduction = [(Adjusted Mean of No Intervention Group – Adjusted Mean of Intervention Group)/Adjusted Mean of No Intervention Group]\*100.

Descriptive statistics (n, mean, SD, SE, median, minimum, maximum) of the number of bleeding sites associated with abutment teeth will be provided at Baseline, Week 6 and Week 12

visits by treatment group (and overall for Baseline only) for the mITT population ([Table 14.2.3.2.1](#)).

The raw mean and SE of the number of bleeding sites (whole mouth and associated with abutment teeth) will be presented graphically over time for each treatment group in [Figure 14.2.2](#) (mITT population).

The number of bleeding sites associated with abutment teeth will be listed by subject and visit in [Listing 16.2.6.7.1](#) for all randomized subjects.

#### **4.5.2.4 MGI score associated with abutment teeth at Week 6 and Week 12**

At each post-baseline visit, the MGI score associated with abutment teeth will be analyzed using an ANCOVA model with treatment group, gender and denture material type (acrylic or cobalt chrome) factors and the baseline MGI score (associated with abutment teeth) as a covariate. For the analysis of MGI the stratification factor of MGI will not be included as the baseline value of MGI is included as a covariate. The adjusted means and SEs of the two treatment groups together with the treatment difference, SE, 95% confidence interval of the difference, between-group p-value and the proportionate reduction will be provided in [Table 14.2.4.2.2](#) for the mITT population.

The proportionate reduction will be calculated as:

- Proportionate reduction = [(Adjusted Mean of No Intervention Group – Adjusted Mean of Intervention Group)/Adjusted Mean of No Intervention Group]\*100.

Descriptive statistics (n, mean, SD, SE, median, minimum, maximum) of the MGI score will be provided at Baseline, Week 6 and Week 12 visits by treatment group (and overall for Baseline only) for the mITT population ([Table 14.2.4.2.1](#)). The raw mean and SE of the MGI score (whole mouth and associated with abutment teeth) will be presented graphically over time for each treatment group in [Figure 14.2.3](#) (mITT population).

Abutment teeth are indicated in the listing of MGI ([Listing 16.2.6.2](#)). The MGI score associated with abutment teeth will be listed by subject and visit in [Listing 16.2.6.7.1](#) for all randomized subjects.

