### **12.2.8 Exploratory Analyses**

The following endpoints are all considered exploratory. The analysis of these endpoints will be performed in a similar manner to the primary or secondary analysis described above.

***Unless indicated otherwise, the following endpoints will be analyzed using the same ANCOVA model with mITT population as used for the primary or secondary analysis.***

- BI associated with abutment teeth at 6 and 12 weeks.
- Number of bleeding sites associated with abutment teeth at 6 and 12 weeks.
- TPI associated with abutment teeth (overall and interproximal) at 6 and 12 weeks.

- CI associated with abutment teeth at 6 and 12 weeks.
- ODI associated with abutment teeth at 6 and 12 weeks.
- OHI associated with abutment teeth at 6 and 12 weeks.
- MGI associated with abutment teeth at 6 and 12 weeks. MGI score will be calculated as the average index associated with the abutment teeth only. At each post-baseline visit, the MGI score will be analyzed using an ANCOVA model with treatment, gender and denture material type (acrylic or cobalt chrome) as factors and baseline MGI score as a covariate. As baseline MGI score is included as a covariate, baseline mean overall MGI score (low, high) is not required. Adjusted means of the two treatments, the proportionate reduction for each treatment group, and the treatment difference will be provided together with 95% CI and P-values.
- Cleaning Perceptions Questionnaire at 6 and 12 weeks will be summarized and listed. Additional details of the proposed statistical analysis will be documented in the RAP.
- RPD photographs - No analysis will be performed on these photographic images. These will be incorporated into the clinical study report for illustration of the PDCI scale only.

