### **3.2 Subgroups/Stratifications**

Eligible subjects will be stratified based on denture material type (acrylic or cobalt chrome) and baseline mean overall MGI score (Low:  $\leq 2.0$ /High:  $> 2.0$ ) to ensure a balance in treatments across the strata, and then randomized into one of two treatment groups (Intervention Group/No Intervention Group).

There will be four strata according to denture material type (acrylic or cobalt chrome) and baseline mean overall MGI score (Low:  $\leq 2.0$ /High:  $> 2.0$ ):

- Stratum 1: Denture material is acrylic, Baseline MGI  $\leq 2.0$
- Stratum 2: Denture material is acrylic, Baseline MGI  $> 2.0$
- Stratum 3: Denture material is cobalt chrome, Baseline MGI  $\leq 2.0$
- Stratum 4: Denture material is cobalt chrome, Baseline MGI  $> 2.0$

The primary and secondary analysis will include gender (Male/Female), denture material type (acrylic or cobalt chrome) and mean baseline MGI (Low:  $\leq 2.0$ /High:  $> 2.0$ ) as factors, with the exception of the analysis of MGI, for which the stratification factor of MGI will not be included as the baseline value of MGI will be included as a covariate.

No subgroup analyses are planned for this study.

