##### **4.4.2.2 MGI Score at Week 6 and Week 12**

The MGI score for each subject will be calculated as the average index value over all tooth sites scored as follows:

- MGI Score = Sum of index values over all evaluable tooth sites/Number of evaluable tooth sites.

The MGI score has a range of 0 to 4.

The MGI will be assessed for the facial and lingual/palatal gingiva of all scorable teeth, four sites per tooth (facial surface - papilla and margin; lingual/palatal surface - papilla and margin).

The MGI will be assessed by the same examiner on all evaluable teeth at Baseline (Visit 2), Week 6 (Visit 3) and Week 12 (Visit 4).

The MGI scoring system is described in [Table 4-3](#).

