##### **4.4.3.4 MGI score associated with abutment teeth at Week 6 and Week 12**

The MGI scoring system is described in [Section 4.4.2.2](#). The MGI score associated with abutment teeth will be calculated as the average index value associated with abutment teeth only.

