#### **4.5.2.5 Overall TPI score associated with abutment teeth at Week 6 and Week 12**

At each post-baseline visit, the Overall TPI score associated with abutment teeth will be analyzed using an ANCOVA model with treatment group, gender, denture material type (acrylic or cobalt chrome), and baseline mean overall MGI score (low, high) as factors and the baseline Overall TPI score (associated with abutment teeth) as a covariate. The adjusted means and SEs of the two treatment groups together with the treatment difference, SE, 95% confidence interval of the difference and between-group p-value will be provided in [Table 14.2.5.2.2](#) for the mITT population.

Descriptive statistics (n, mean, SD, SE, median, minimum, maximum) of the Overall TPI score associated with abutment teeth will be provided at Baseline, Week 6 and Week 12 visits by treatment group (and overall for Baseline only) for the mITT population ([Table 14.2.5.2.1](#)).

The raw mean and SE of the Overall TPI score (whole mouth and associated with abutment teeth) will be presented graphically over time for each treatment group in [Figure 14.2.4](#) (mITT population).

Abutment teeth are indicated in the listing of TPI ([Listing 16.2.6.3](#)). The Overall TPI score associated with abutment teeth will be listed by subject and visit in [Listing 16.2.6.7.1](#) for all randomized subjects.

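### The abutment-teeth MGI model leaves out the whole-mouth MGI randomisation stratum for a reason that fits only the whole-mouth MGI model; the cost is slight conservatism in an exploratory analysis

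*SAP*

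**What the plan says.** **Randomisation.** SAP 3.2: "Eligible subjects will be stratified based on denture material type (acrylic or cobalt chrome) and baseline mean overall MGI score", with the MGI cut at 2.0. Together with denture material this gives four strata. SAP 3.2 states the MGI exception (stratum left out of the model) for the primary and secondary analyses.

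**The two MGI scores.** The whole-mouth score is defined in SAP 4.4.2.2: "MGI Score = Sum of index values over all evaluable tooth sites/Number of evaluable tooth sites". The abutment score is defined in SAP 4.4.3.4: "The MGI score associated with abutment teeth will be calculated as the average index value associated with abutment teeth only".

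**The abutment MGI model.** SAP 4.5.2.4 has treatment, gender and denture material as factors, plus "the baseline MGI score (associated with abutment teeth) as a covariate. For the analysis of MGI the stratification factor of MGI will not be included". Its stated ground for the omission is that a baseline MGI value is already in the model.

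**The protocol.** Section 12.2.8, on abutment MGI: "As baseline MGI score is included as a covariate, baseline mean overall MGI score (low, high) is not required". The sentences before it define the score on abutment teeth and then list baseline MGI as the covariate, without saying whether that baseline is abutment or whole-mouth.

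**The other abutment models.** Bleeding sites, overall and interproximal TPI, CI, ODI and OHI (SAP 4.5.2.3 and 4.5.2.5 to 4.5.2.9) all keep the whole-mouth stratum beside an abutment baseline. For overall TPI, for example: "baseline mean overall MGI score (low, high) as factors and the baseline Overall TPI score (associated with abutment teeth) as a covariate". Abutment BI (SAP 4.5.2.2) does not keep it and gives no reason.

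**The concern.** In the whole-mouth MGI model (SAP 4.5.1.2), the low/high stratum is a cut of the covariate itself. Once the continuous score is in the model, the stratum adds nothing unless the relation is non-linear, so leaving it out is reasonable.

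The abutment section reuses that argument with a different covariate. A subject's abutment mean does not determine which side of 2.0 the whole-mouth mean falls on, so the model no longer conditions on one of the two stratification factors.

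Stratified allocation balances the arms on the stratum. If the stratum predicts outcome beyond the covariate and is left out, its variance stays in the residual. The model standard error then overstates the true sampling variability and the confidence interval is too wide. At stake is some sharpness in an exploratory comparison on the teeth that the protocol's introduction singles out as most at risk from a partial denture.

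**Working it through.** The documents state no figure on this point, and they give no SD or correlation for abutment MGI. The check is therefore a comparison of definitions, followed by simulation on assumed inputs.

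**1. Are covariate and stratum the same variable?** No. The stratum comes from the mean over all evaluable sites; the covariate is the mean over abutment sites. Entry requires at least 2 scorable abutment teeth (Protocol 5.2), and MGI has four sites per tooth, so the covariate can rest on 2 × 4 = 8 sites.

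**2. How much of the stratum does the covariate carry?** The share of stratum variance not captured linearly is 1 − r², where r is the correlation of the covariate with the low/high indicator. Whole-mouth MGI was simulated within the entry range 1.75–2.30, as uniform or truncated normal.
- Whole-mouth covariate: r is 0.83–0.86, so r² is 0.68–0.74. The remainder is only the effect of dichotomising, because the stratum is a function of this covariate.
- Abutment covariate: r is roughly ρ × 0.83 to ρ × 0.86, where ρ is the abutment/whole-mouth correlation (assumed 0.3 to 0.9).

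| ρ | Stratum variance not captured |
|---|---|
| 0.3 | 93–94% |
| 0.5 | 81–83% |
| 0.7 | 64–67% |
| 0.9 | 40–45% |

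At ρ = 0.5 with uniform scores, for instance, r = 0.433 and 1 − 0.433² = 0.81.

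**3. Effect on the standard error, in MGI units.** Assumed: 128 subjects (the SAP's evaluable target), permuted blocks within four strata, whole-mouth SD 0.14 truncated to 1.75–2.30, abutment noise SD 0.21 (8 sites), residual SD 0.25, 3,000 runs. The slope is the effect of whole-mouth MGI on outcome beyond the abutment covariate.

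| Slope | SE without / with stratum | Ratio | 95% interval coverage without stratum |
|---|---|---|---|
| 0.5 | 0.0455 / 0.0449 | 1.013 | 0.959 |
| 1.0 | 0.0483 / 0.0460 | 1.050 | 0.957 |
| 1.5 | 0.0527 / 0.0480 | 1.098 | 0.969 |

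A repeat run gave inflation of 1.3%, 4.8% and 10.0%. At slope 0.25 it is 0.1–0.2%, and at slope 0 it is nil. With twice the abutment sites (noise SD 0.21/√2 = 0.148), slopes of 1.0 and 1.5 give 3.5% and 7.4%.

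**4. Effect in SD units, under no treatment effect.** Outcome = 0.5 × abutment baseline + ψ × standardised whole-mouth MGI + error of SD 1; 128 subjects, blocks of 4, 4,000 runs. Monte Carlo error on the rejection rate is √(0.05 × 0.95 / 4000) ≈ 0.003.

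| ρ | ψ | SE without / with | Ratio | Type I error without / with |
|---|---|---|---|---|
| 0.5 | 0 | 0.1777 / 0.1779 | 0.999 | 0.049 / 0.049 |
| 0.5 | 0.3 | 0.1840 / 0.1805 | 1.02 | 0.047 / 0.054 |
| 0.5 | 0.6 | 0.2010 / 0.1874 | 1.073 | 0.039 / 0.051 |
| 0.8 | 0 | 0.1776 / 0.1779 | 0.998 | 0.048 / 0.047 |
| 0.8 | 0.3 | 0.1806 / 0.1797 | 1.005 | 0.047 / 0.049 |
| 0.8 | 0.6 | 0.1888 / 0.1844 | 1.024 | 0.045 / 0.048 |

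The mean treatment estimate is never more than 0.0034 from zero. In the worst row the empirical SD of the estimate is 0.1894 without the stratum and 0.1869 with it, a ratio of 1.013. Most of the 7.3% is therefore the model overstating its own uncertainty, and little of it is a real loss of precision.

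**5. Abutment BI.** Protocol 12.2.8 calls for the same ANCOVA model as the primary or secondary analysis unless indicated otherwise. The BI model there includes the MGI stratum. SAP 4.5.2.2 lists treatment, gender and denture material only, and Table 5-1 records no such change.

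**The case against.** The strongest answer is that this hardly matters, and most of that stands. The endpoint is exploratory, study success is defined on BI at 12 weeks alone, and no primary or secondary model is touched. The error runs in the safe direction.

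The upper end of the size range also needs an implausible input. A slope of 1.5 means that each unit of baseline whole-mouth MGI adds 1.5 units of 12-week abutment MGI on the same 0–4 scale, after a prophylaxis to zero plaque. Nothing in the documents supports that. A noise SD of 0.21 likewise puts every subject at the entry minimum of 2 abutment teeth.

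Stronger readings that a reader might infer, and that the documents do not support:
- *The comparison is biased or its error rate inflated.* Neither simulation shows this.
- *The covariate carries none of the stratum.* Evaluable abutment sites are part of the whole-mouth mean, so it carries some.
- *The protocol plainly makes the same substitution, or the SAP plainly contradicts it.* Protocol 12.2.8 does not say which baseline MGI it means. The preceding sentences suggest abutment. If whole-mouth was meant, the protocol's reason is sound and the SAP introduced the substitution.

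What the objection does not rescue is the stated reason. It is the SAP's only ground for treating abutment MGI differently from the six abutment models that keep the stratum.

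**Conclusion.** The point holds as a minor one. The reason given in SAP 4.5.2.4 for leaving out the MGI stratum is not correct for abutment MGI, because the covariate only partly represents the whole-mouth stratum. The consequence is a test that is valid or slightly conservative, with an unbiased estimate.

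A modest effect of whole-mouth MGI beyond abutment MGI (slope up to 0.5) makes the standard error too large by about 0–1%. A slope of 1.0 gives about 3–5%, and 7–10% is an extreme case. These sizes rest on assumed SDs, slopes and correlations; only the sample size, the MGI entry range and the cut at 2.0 come from the documents.

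The omission in the abutment BI model is the clearer inconsistency, since it has no stated reason and departs from Protocol 12.2.8.

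**What to change.** - **SAP 4.5.2.4:** fit treatment, gender, denture material and baseline mean overall MGI (low, high) as factors, with baseline abutment MGI as covariate. Delete the sentence saying that the stratum is not included.
- **Protocol 12.2.8:** make the matching change and state that the covariate is the abutment baseline. If the protocol is not amended, record the change in SAP Table 5-1.
- **SAP 4.5.2.2 (abutment BI):** add the same factor, so that all abutment-teeth models include it.
- **SAP 4.5.1.2 (whole-mouth MGI):** leave unchanged.

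The cost is one model term in each of two exploratory models. With 128 subjects, residual degrees of freedom go from 128 − 5 = 123 to 128 − 6 = 122. No new data are needed. If whole-mouth MGI turns out to add nothing, the standard error is essentially unchanged (ratios of 0.998–0.999 in the simulation).

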#### **4.5.2.5 Overall TPI score associated with abutment teeth at Week 6 and Week 12**

At each post-baseline visit, the Overall TPI score associated with abutment teeth will be analyzed using an ANCOVA model with treatment group, gender, denture material type (acrylic or cobalt chrome), and baseline mean overall MGI score (low, high) as factors and the baseline Overall TPI score (associated with abutment teeth) as a covariate. The adjusted means and SEs of the two treatment groups together with the treatment difference, SE, 95% confidence interval of the difference and between-group p-value will be provided in [Table 14.2.5.2.2](#) for the mITT population.

Descriptive statistics (n, mean, SD, SE, median, minimum, maximum) of the Overall TPI score associated with abutment teeth will be provided at Baseline, Week 6 and Week 12 visits by treatment group (and overall for Baseline only) for the mITT population ([Table 14.2.5.2.1](#)).

The raw mean and SE of the Overall TPI score (whole mouth and associated with abutment teeth) will be presented graphically over time for each treatment group in [Figure 14.2.4](#) (mITT population).

Abutment teeth are indicated in the listing of TPI ([Listing 16.2.6.3](#)). The Overall TPI score associated with abutment teeth will be listed by subject and visit in [Listing 16.2.6.7.1](#) for all randomized subjects.

#### **4.5.2.6 Interproximal TPI score associated with abutment teeth at Week 6 and Week 12**

At each post-baseline visit, the Interproximal TPI score associated with abutment teeth will be analyzed using an ANCOVA model with treatment group, gender, denture material type (acrylic or cobalt chrome), and baseline mean overall MGI score (low, high) as factors and the baseline Interproximal TPI score (associated with abutment teeth) as a covariate. The adjusted means and SEs of the two treatment groups together with the treatment difference, SE, 95% confidence interval of the difference and between-group p-value will be provided in [Table 14.2.6.2.2](#) for the mITT population.

Descriptive statistics (n, mean, SD, SE, median, minimum, maximum) of the Interproximal TPI score associated with abutment teeth will be provided at Baseline, Week 6 and Week 12 visits by treatment group (and overall for Baseline only) for the mITT population ([Table 14.2.6.2.1](#)).

Abutment teeth are indicated in the listing of TPI ([Listing 16.2.6.3](#)). The Interproximal TPI score associated with abutment teeth will be listed by subject and visit in [Listing 16.2.6.7.1](#) for all randomized subjects.

#### **4.5.2.7 CI score associated with abutment teeth at Week 6 and Week 12**

At each post-baseline visit, the CI score associated with abutment teeth will be analyzed using an ANCOVA model with treatment group, gender, denture material type (acrylic or cobalt chrome), and baseline mean overall MGI score (low, high) as factors and the baseline CI score (associated with abutment teeth) as a covariate. The adjusted means and SEs of the two treatment groups together with the treatment difference, SE, 95% confidence interval of the difference and between-group p-value will be provided in [Table 14.2.8.2.2](#) for the mITT population.

Descriptive statistics (n, mean, SD, SE, median, minimum, maximum) of the CI score associated with abutment teeth will be provided at Baseline, Week 6 and Week 12 visits by treatment group (and overall for Baseline only) for the mITT population ([Table 14.2.8.2.1](#)).

The raw mean and SE of the CI score (whole mouth and associated with abutment teeth) will be presented graphically over time for each treatment group in [Figure 14.2.6](#) (mITT population).

Abutment teeth are indicated in the listing of OHI components – CI and ODI ([Listing 16.2.6.5](#)). The CI score associated with abutment teeth will be listed by subject and visit in [Listing 16.2.6.7.2](#) for all randomized subjects.

#### **4.5.2.8 ODI score associated with abutment teeth at Week 6 and Week 12**

At each post-baseline visit, the ODI score associated with abutment teeth will be analyzed using an ANCOVA model with treatment group, gender, denture material type (acrylic or cobalt chrome), and baseline mean overall MGI score (low, high) as factors and the baseline ODI score (associated with abutment teeth) as a covariate. The adjusted means and SEs of the two treatment groups together with the treatment difference, SE, 95% confidence interval of the difference and between-group p-value will be provided in [Table 14.2.9.2.2](#) for the mITT population.

Descriptive statistics (n, mean, SD, SE, median, minimum, maximum) of the ODI score associated with abutment teeth will be provided at Baseline, Week 6 and Week 12 visits by treatment group (and overall for Baseline only) for the mITT population ([Table 14.2.9.2.1](#)).

The raw mean and SE of the ODI score (whole mouth and associated with abutment teeth) will be presented graphically over time for each treatment group in [Figure 14.2.7](#) (mITT population).

Abutment teeth are indicated in the listing of OHI components – CI and ODI ([Listing 16.2.6.5](#)). The ODI score associated with abutment teeth will be listed by subject and visit in [Listing 16.2.6.7.2](#) for all randomized subjects.

#### **4.5.2.9 OHI score associated with abutment teeth at Week 6 and Week 12**

At each post-baseline visit, the OHI score associated with abutment teeth will be analyzed using an ANCOVA model with treatment group, gender, denture material type (acrylic or cobalt chrome), and baseline mean overall MGI score (low, high) as factors and the baseline OHI score (associated with abutment teeth) as a covariate. The adjusted means and SEs of the two treatment groups together with the treatment difference, SE, 95% confidence interval of the difference and between-group p-value will be provided in [Table 14.2.10.2.2](#) for the mITT population.

Descriptive statistics (n, mean, SD, SE, median, minimum, maximum) of the OHI score associated with abutment teeth will be provided at Baseline, Week 6 and Week 12 visits by treatment group (and overall for Baseline only) for the mITT population ([Table 14.2.10.2.1](#)).

The raw mean and SE of the OHI score (whole mouth and associated with abutment teeth) will be presented graphically over time for each treatment group in [Figure 14.2.8](#) (mITT population).

The OHI score associated with abutment teeth will be listed by subject and visit in [Listing 16.2.6.7.2](#) for all randomized subjects.

